9.11 Definition of End of Study

The end of study date is the date of final EMCAT assessment or final interview, whichever comes later.

9.12 Study sequence

- 1. Potential participants will be identified by clinical members of the research team during routine care.
- 2. The clinical team members will invite potential participants to participate on the day of their treatment.
- 3. Potential participants will be provided with a written information pack, and given time to read this and discuss it.
- 4. The investigator will take informed consent from the participant at that point, if the participant feels they have had sufficient time to consider taking part.

- 5. At the point of recruitment, a member of the research team will assist the participant in downloading the EMCAT app and enabling push notifications.
- 6. At the point of recruitment, prior to the treatment, the participant will complete the full-length (11-item) PEM part 2 via the EMCAT app, and a single EMCAT assessment.
- 7. Over the next 12 weeks, participants will complete daily PEM EMCAT questionnaires (if they choose to) when prompted by email or push notification.
- 8. In addition, at 6 and 12 weeks, participants will be asked to complete the full-length PEM part 2 via the app, separately.
- 9. At 12 weeks, participants will also be asked to complete the UES via the app. Participants who do not respond with 7 days will be contacted via email or telephone and asked if they would like to return UES responses either via email or over the telephone. The method of UES response (app/email/telephone) will be recorded, if not via the ECMAT platform.
- 10. At 12 weeks, notifications will stop for all participants except those who underwent steroid injection for TBOA these participants will continue to receive EMCAT notifications twice weekly for a further 12 weeks.
- 11. For participants undergoing steroid injection for TBOA or open CTD, at the 24-week timepoint, a clinical member of the research team will review the participant's medical record and record follow-up appointment dates and (for those who underwent open CTD) whether the follow up resulted in a change of management.
- 12. Three independent clinicians will review de-identified EMCAT trajectories and appointment dates for patients who underwent open CTD, and predict whether each participant required a change in management.
- 13. We will identify and approach 10 patients and 10 clinicians with invitations to take part in semistructured interviews – interviews will take place no later than 14 days after finishing use of the EMCAT platform.
- 14. Interview participants will be provided with additional written information and time to consider their involvement in the interviews, a member of the research team will then take informed consent for participation in the interviews remotely.
- 15. We will conduct interviews with the participants using the Microsoft Teams videoconferencing platform. The audio of these interviews will be recorded, transcribed and then de-identified (all identifiable text redacted and the transcript assigned a study number). Recordings will then be deleted. Interviews are expected to last approximately 20 minutes.
- 16. Participants will not be followed up after interview.
- 17. We will notify all participants when the results of this study have been made available in the public domain.
- 18. Personal data will be held securely for a maximum three-year period, and then destroyed, with the exception of email addresses which will be deleted as soon as participants have been notified that the results are in the public domain. De-identified interview transcripts will be held

for 7 years and then destroyed. Anonymised research data from Stream 1 and 2 will be made publicly available to support future methodological work.

10 SAFETY REPORTING

This study is not likely to result in any adverse events.

11 STATISTICS AND ANALYSIS

11.3 Statistical Analysis Plan (SAP)

The plan for the statistical analysis of the study are outlined below. There is not a separate SAP document in use for the trial.

11.4 Description of the Statistical Methods

The hypotheses outlined in the primary and secondary objectives will be tested with mixed-effects linear modelling. These models will comprise: EMCAT score (continuous dependent variable on a logit scale, derived from a graded response model); participant number (random intercept); age, sex, and baseline score (fixed effects); and an interaction term between time (number of days following the intervention) and treatment allocation. Marginal means will be derived from these models and between-group differences calculated at daily timepoints after Tukey adjustment for multiplicity. This will be performed with the *emmeans* R package, or equivalent software. For each comparison, marginal means will be plotted, and differences compared to a minimal important difference (MID) estimate of half a standard deviation of baseline scores. Clinically and statistically significant (at the 5% level) differences will be compared to those predicted (see section 6).

EMCAT completion rates (number of completed response sets divided by number of invitations), response times, and UES scores will be analysed through descriptive statistics. The UES was originally intended to measure 6 user engagement constructs, but subsequent studies have suggested that it follows a 4-factor structure. Items of the UES will be grouped into the 4 subscales described by O'Brein et al, to measure: focused attention, aesthetic appeal, perceived usability and reward⁵.

The criterion validity of the EMCAT scores against the full-length PEM scores will be assessed by comparing pairs of EMCAT scores and full-length PEM scores that were obtained from the same participant on the same day. Comparison will be made by calculating Pearson's correlation coefficient, mean absolute error, root mean squared error and the Bland-Altman method⁶.

In Stream 2, three independent clinicians will review EMCAT trajectories (presented as time series plots) and follow-up appointment dates for participants that underwent open CTD. They will be asked to predict whether a change in management was required at the follow-up appointment. We will calculate inter-rater reliability of these assessments (Fleiss' kappa) and, for each clinician, the accuracy, sensitivity, specificity, positive predictive value and negative predictive value of their predictions against the reference standard (whether or not the patient received a change in management).

The 24-week EMCAT trajectory for patients undergoing steroid injection for TBOA will be plotted as a time series, with follow-up appointment dates overlain. These plots will be inspected and presented to

give an impression as to whether follow-up appointments coincide with peaks in symptom severity. This will not be formally tested with quantitative methods.

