6. OBJECTIVES AND OUTCOME MEASURES

Objectives	Outcome Measures	Timepoint(s) of evaluation of this outcome measure (if applicable)
Primary Objective		
1. Compare the recovery trajectories of patients undergoing percutaneous needle fasciectomy (PNF) to patients undergoing limited fasciectomy (LF), to test whether EMCAT can detect different recovery trajectories over a 12-week period, with less severe post-treatment symptoms in the PNF group within the first 4 weeks.	The PEM, administered via EMCAT.	Trajectories will be plotted and compared over a 12-week period.
Secondary Objectives		
2. Compare the recovery trajectories of other groups that are expected to differ over a 12-week period. Specifically, we will test the following hypotheses, which are based on the researchers' clinical experience:	The PEM, administered via EMCAT.	Trajectories will be plotted and compared over a 12-week period.
 Steroid injection results in less severe post-treatment symptoms than trapeziectomy, within the first 4 weeks 		
 Trapeziometacarpal arthroplasty results in less severe post- treatment symptoms than trapeziectomy, within the first 4 weeks 		
 Minimally invasive (endoscopic or percutaneous) CTD results in less severe post-treatment symptoms than open CTD, within the first 2 weeks 		
 The difference in the recovery of groups undergoing open release vs steroid injection for trigger finger are not clinically significant over the first 2 weeks 		
The objective is to test EMCAT's ability to differentiate between recovery trajectories that are expected to differ, rather than to prove or disprove that differences in recovery trajectory exist. The clinical comparisons are a vehicle for testing the measurement properties of EMCAT. Here, the threshold for clinically significant difference is approximated as half a standard deviation of baseline scores of groups being compared. Statistical significance is taken at the 5% level. By symptom severity, we mean PEM EMCAT scores, where a higher (poorer) score reflects more severe symptoms (a poorer level of hand health).		

	UES scores,	12-week follow-up
3. Assess the usability of the EMCAT platform	response rates, response times, and semi- structured interviews	
4. Assess the criterion validity of EMCAT against the full-length PEM by comparing scores at baseline, 6 weeks, and 12 weeks	Full-length PEM scores and EMCAT PEM scores	Baseline, 6-week and 12-week follow-up
Exploratory Objectives		

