7. STUDY DESIGN

We will perform a mixed-methods cohort study to explore the feasibility of EMCAT for measuring between-group differences in postoperative recovery, its potential to guide follow-up type (face-to-face, telemedicine or patient-initiated) in open carpal tunnel decompression, and its potential to guide follow-up timing after steroid injection for TBOA. The study setting will be NHS hospitals in the England, Scotland and Wales.

Our primary objective is to use EMCAT to compare the recovery trajectories of patients undergoing PNF and LF for Dupuytren's disease. We expect to see a difference in recovery trajectory over a 12-week period, with patients undergoing PNF showing less severe symptoms than those undergoing LF over the first 4 weeks. To meet this objective, we will recruit 396 participants (198 undergoing PNF and 198 undergoing LF), who will be followed up for a 12-week period with daily EMCAT assessments.

To address our secondary objectives, we will simultaneously recruit patients undergoing:

- Steroid injection for TBOA
- Steroid injection for trigger finger
- Trapeziectomy for TBOA
- Arthroplasty for TBOA
- Surgical release of trigger finger
- Open CTD
- Minimally invasive (endoscopic or percutaneous) CTD

We will recruit as many participants as we can in these groups, within the limits of the study timing and funding, and up to a maximum of 198 per group. We will use all collected EMCAT data to test the following hypotheses:

- Steroid injection results in less severe post-treatment symptoms than trapeziectomy, within the first 4 weeks
- Trapeziometacarpal arthroplasty results in less severe post-treatment symptoms than trapeziectomy, within the first 4 weeks
- Minimally invasive (endoscopic or percutaneous) CTD results in less severe post-treatment symptoms than open CTD, within the first 2 weeks
- The difference in the recovery of groups undergoing open release vs steroid injection for trigger finger are not clinically significant over the first 2 weeks

The objective is to test EMCAT's ability to differentiate between recovery trajectories that are expected to differ, rather than to prove or disprove that differences in recovery trajectory exist. The clinical comparisons are a vehicle for testing the measurement properties of EMCAT.

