9.4 Enrolment

This study does not involve randomisation. At the point of recruitment, a member of the research team will assist the participant in downloading the EMCAT app and enabling push notifications.

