9.7 Study visit

At the point of recruitment, a member of the research team will assist the participant in downloading the EMCAT app and enabling push notifications. A spreadsheet will be updated with the participants study number, eligibility status, reason for exclusion if applicable, age, sex, ethnicity, employment status, hand dominance, as well as the treatment they are undergoing, the date and the timing of the EMCAT scheduling.

The participant will complete a single full-length PEM assessment and an EMCAT PEM assessment via the application at this appointment.

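### The non-randomised PNF versus LF model adjusts only for age, sex and baseline score, so case-mix differences in other recorded variables may remain in the contrast used to judge EMCAT

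*Protocol*

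**What the plan says.** - **Allocation.** Section 9.4: "This study does not involve randomisation".
- **Model.** Section 11.4 specifies one mixed-effects linear model for the primary and secondary hypotheses. It has a participant random intercept, a time-by-treatment interaction, and "age, sex, and baseline score (fixed effects"). No other adjustment covariate is named.
- **Data collected.** Section 9.7 lists "age, sex, ethnicity, employment status, hand dominance, as well as the treatment they are undergoing" among the items recorded at recruitment, and section 12.5 repeats the list. Neither lists the treated side.
- **No other place for the analysis.** Section 11.3: "There is not a separate SAP document in use for the trial". Section 11.10 rules out imputation and sensitivity analyses.
- **Prediction tested.** The primary objective in section 6 expects different trajectories, "with less severe post-treatment symptoms in the PNF group within the first 4 weeks". Section 11.4 then compares the significant differences found with those predicted.
- **Stated purpose.** Section 7 says the aim is to test whether EMCAT can separate trajectories, "rather than to prove or disprove that differences in recovery trajectory exist", and adds: "The clinical comparisons are a vehicle for testing the measurement properties of EMCAT".

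**The concern.** Without randomisation, the PNF and LF groups may differ in ways that affect hand-function scores after treatment. Employment status and whether the dominant hand is treated are plausible examples, because the PEM item shown in Appendix A asks about everyday use of the hand. The protocol already accepts the need for adjustment by including age and sex. It stops there without explanation, although further baseline variables are in hand.

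What is at stake is the inference about the instrument. EMCAT is judged by whether the modelled differences match predictions about treatments. If case mix produced an early gap in favour of PNF, EMCAT would be credited with detecting a treatment difference that the data did not show. If case mix hid the gap, EMCAT would be failed wrongly. The same model serves all five comparisons. One of them, trigger finger, predicts no clinically significant difference, so imbalance could create or break agreement there too.

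Hand dominance raises a second, smaller problem. It is informative mainly in combination with the treated side, which is not a listed data item. Bilateral treatment is excluded (section 8.3), so treated side would have a single value per participant.

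**Working it through.** **1. The plan's own figure (section 11.5).** Inputs: difference 0.35, SD 1, power 90%, significance level 5%. Sidedness is not stated, but two-sided reproduces the figure.

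n per group = 2 × (1.960 + 1.282)² / 0.35² = 2 × 10.51 / 0.1225 ≈ 171.6, which rounds up to 172, or 344 in total. Power at 172 per group is 90.1%. The target follows from 344 × 1.15 ≈ 396. The point made here does not change the sample size.

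**2. Size of a possible bias.** The documents give no association of any of the three variables with treatment or with score, so every input to this step is an assumption. For an omitted binary covariate,

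bias = g × d,

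where g is its effect on the score in SD units and d is the difference in its prevalence between groups. Strictly, both should be taken after adjustment for age, sex and baseline score. The values below are not, so they overstate the bias to the extent that those covariates already absorb it.

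| g (SD) | d = 0.10 | d = 0.20 | d = 0.30 |
|---|---|---|---|
| 0.2 | 0.02 | 0.04 | 0.06 |
| 0.3 | 0.03 | 0.06 | 0.09 |
| 0.5 | 0.05 | 0.10 | 0.15 |

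Relative to 0.35, the extremes are 0.02 / 0.35 = 6% and 0.15 / 0.35 = 43%. With g = 0.1 and d = 0.05 the bias is 0.005 SD, about 1%.

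**3. What that would do to a test.** For a simple two-group comparison at 172 per group, the standard error is √(2/172) = 0.108 SD.

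- With no true difference, the chance of a significant result (nominally 5%) is 5.0% at a bias of 0.005, 5.4% at 0.02, 6.6% at 0.04, 15.3% at 0.10 and 28.5% at 0.15.
- With a true difference of 0.35 and bias in the opposite direction, the net difference is 0.25 or 0.20. Power is then Φ(0.25/0.108 − 1.96) ≈ 64% or Φ(0.20/0.108 − 1.96) ≈ 46%.

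These rates only illustrate scale. The planned analysis uses repeated daily scores with Tukey-adjusted contrasts, which this calculation does not reproduce.

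**4. Whether another part of the plan covers it.** Section 11.10 will describe how missingness relates to other variables. That describes non-response and does not adjust the treatment contrast. No other section supplies a fuller model.

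**The case against.** The strongest reply has five parts.

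- **Confounding is not demonstrated.** A reader might infer that avoidable confounding definitely sits in the primary estimate. The documents do not support that. Being recorded does not make a variable a confounder. It must relate to both treatment received and post-treatment score, given age, sex and baseline score, and the protocol shows this for none of the three. It does not even describe how treatment is chosen. This part stands, and it is why the point is put as *may remain*.
- **Baseline score already does much of the work.** Effects of work or dominance on hand function should show in the pre-treatment PEM, which is in the model. This stands in part: an effect that arises only during recovery would not be captured at baseline.
- **The purpose is measurement, not a treatment effect.** Sections 6 and 7 say so, and this lowers the stakes. It does not remove them, because section 11.4 judges EMCAT against predictions about treatments.
- **The extra covariates would not settle the matter.** Contracture severity and earlier treatment plausibly influence the choice of procedure (a judgement, not a statement in the protocol), and neither is recorded. It would be wrong to infer that adding the three variables yields an unconfounded contrast.
- **There are practical limits.** Ethnicity may be sparse in secondary groups, which have no minimum size. Dominance cannot be used fully until treated side is recorded.

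A reader might also infer that these variables predict app response and so threaten the missing-data assumption. Nothing in the documents establishes that, and the point does not rest on it.

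**Conclusion.** The point holds in a limited form. The comparison is not randomised, the only specified model omits three recorded baseline variables without a reason, and neither a separate SAP nor a sensitivity analysis fills the gap. Case-mix differences may therefore remain in the contrast on which EMCAT is judged.

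The size is unknown. Under the assumed inputs the bias runs from 0.02 to 0.15 SD, which is small at one end and material at the other against a design effect of 0.35 SD. The upper figure pairs both assumed maxima and ignores the existing adjustment for age and baseline score, so it should not be read as an estimate for this trial. Nothing in section 11.4 is miscalculated or self-contradictory. The weakness is a narrow covariate set, fixed without justification, in a plan that offers no way to see whether the answer depends on it.

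**What to change.** 1. In section 11.4, add employment status and whether the treated hand is the dominant one as fixed effects. Add ethnicity in broad categories where group sizes allow.
2. In section 9.7, and the matching list in 12.5, add one spreadsheet field: treated side, left or right.
3. Report the model with age, sex and baseline score alongside the fuller one, so that readers can see whether the conclusion moves.
4. If the sponsor prefers to keep the present model as primary, prespecify the fuller model as a supporting analysis and amend section 11.10, which now excludes sensitivity analyses.
5. In either case, state that confounding by indication from unrecorded factors, such as disease severity and prior treatment, remains a limitation.

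**Cost.** A short text change and one data field. Statistically, it uses a few degrees of freedom out of about 344 evaluable patients in the primary comparison. Because no imputation is planned, occasional participants with a missing covariate would drop out of the fuller model.

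### Section 11.4 adjusts for baseline score, age and sex with time-constant effects only, so the daily PNF–LF differences are only partly adjusted if a covariate's effect changes during recovery

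*Protocol*

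**What the plan says.** Protocol section 11.4 fixes one model for the primary and secondary hypotheses. Besides the participant random intercept it contains "age, sex, and baseline score (fixed effects); and an interaction term between time (number of days following the intervention) and treatment allocation". From this model, marginal means are derived and "between-group differences calculated at daily timepoints after Tukey adjustment for multiplicity". The differences are then set against a "minimal important difference (MID) estimate of half a standard deviation of baseline scores" and the 5% level.

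Four other places matter here:
- Section 6: the primary objective is "to test whether EMCAT can detect different recovery trajectories over a 12-week period", with PNF expected to be less severe in the first 4 weeks. The secondary hypotheses use windows of 2 or 4 weeks.
- Section 9.4: "This study does not involve randomisation".
- Section 11.3: "There is not a separate SAP document in use for the trial". The model in 11.4 is therefore the full specification.
- Section 11.10: no sensitivity analyses are planned.

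**The concern.** A main effect for baseline score gives it one coefficient for the whole follow-up. The model then assumes that the pre-treatment score predicts the score on day 1 after a procedure exactly as it predicts the score on day 84. Recovery makes that doubtful. The immediate effect of the procedure may swamp pre-treatment severity at first, or pre-treatment severity may fade as a predictor once the hand has healed.

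In a randomised comparison the resulting bias would average out. Here patients reach PNF or LF by clinical choice, so baseline scores may differ. Any change over time in the baseline coefficient, multiplied by that difference, has only one place to go in the model: the treatment-by-time term. The daily PNF–LF differences, which are compared with the predicted pattern, would then carry part of the case-mix difference. It could imitate an early PNF advantage or hide one. The same applies to age and sex, and to the Objective 2 comparisons.

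**Working it through.** **The plan's own figure.** Section 11.5 uses an effect of 0.35, SD 1, 90% power and the 5% level. Two-sided, n per group = 2 × (1.960 + 1.282)² / 0.35² = 171.6, rounded up to 172, as stated. This figure is not in question. It supplies the group size and a yardstick (0.35) for what follows.

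**Formula.** Let β(t) be the true coefficient of baseline score on day t, β̄ its average over follow-up, and D the LF minus PNF difference in mean baseline score. A model with one baseline coefficient estimates approximately β̄ when data are balanced. The group difference (LF minus PNF) on day t then carries

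bias(t) = D × [β(t) − β̄],

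and PNF minus LF carries the opposite sign. If β changes linearly by C from day 1 to day 84, the midpoint is day 42.5 and the size of the bias is D × C × |42.5 − t| / 83.

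**Inputs.** D and C are assumptions, because the Protocol gives neither. Scores are in SD units, as in section 11.5.

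| D | Change C | Day 1 | Day 14 | Day 28 | Day 84 (opposite sign) |
|---|---|---|---|---|---|
| 0.3 | 0.3 | 0.045 | 0.031 | 0.016 | 0.045 |
| 0.5 | 0.4 | 0.100 | 0.069 | 0.035 | 0.100 |
| 0.5 | 0.5 | 0.125 | 0.086 | 0.044 | 0.125 |

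Example, second row, day 28: 0.5 × 0.4 × 14.5 / 83 = 0.035. Relative to the design effect, the day-1 bias is 0.045/0.35 = 13% to 0.125/0.35 = 36%. By day 28 it is 4% to 12%.

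**Direction.** With LF worse at baseline, a falling coefficient (0.7 to 0.3) gives PNF − LF of about −0.10 on day 1, a spurious PNF benefit. A rising one (0.2 to 0.7) gives about +0.12, against PNF.

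**Effect on the day-1 test.** Further assumptions: random-intercept SD 0.6, residual SD 0.5, scores every third day (29 occasions), linear time, 172 per group, no treatment effect. The variance of the day-1 contrast is about (2/172) × [0.36 + 0.25 × 0.131] = 0.00457, where 0.131 is the end-point leverage of a straight line through 29 points, 2 × 57 / (29 × 30). The SE is 0.068. Simulated rejection rates (2,000 studies per row) agree with this:

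| D, coefficient | Day 1 | Day 14 | Day 28 | Day 1 with baseline-by-time |
|---|---|---|---|---|
| 0.3, 0.6 to 0.3 | 11% | 8% | 6% | 5% |
| 0.5, 0.7 to 0.3 | 32% | 18% | 8% | 6% |
| 0.5, 0.2 to 0.7 | 44% | 23% | 9% | 6% |
| 0.5, constant 0.5 | 5% | 5% | 5% | 5% |

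**Direct check that a main effect does not adjust the interaction.** In one balanced simulated data set (12 weekly scores, D = 0.5, coefficient 0.7 to 0.3, no true effect), the treatment-by-time estimate was −0.149 (SE 0.056) both with and without baseline as a main effect. Adding baseline-by-time moved it to 0.046 (SE 0.056).

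**The case against.** **The aim is to test EMCAT, not treatments.** Sections 6 and 7 say that the comparisons are a vehicle for testing measurement properties. If case mix makes the trajectories diverge, EMCAT detecting this is not a measurement error. That is fair as far as it goes. But 11.4 sets out to adjust for baseline score, and it judges EMCAT by whether the adjusted differences match predictions about treatments. A case-mix remainder could be scored as agreement or as disagreement, so the purpose statement does not dispose of the point.

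**The bias is below the minimal important difference.** This stands. If a difference must be both significant and at least 0.5 SD to count, a simulation of the same design (2,000 runs, four scenarios) gave no false PNF benefit on days 1, 14, 28 or 84. If significance alone counts, the inflation in the table remains. The artefact can also add to or subtract from a real difference.

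**All inputs are assumed, and day 1 is the worst early day.** Both stand. The bias needs a baseline difference and a changing coefficient, and it shrinks through the 4-week window. No size has been worked out for age or sex.

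**Stronger readings to avoid.** A reader might infer that the trajectory comparison is almost bound to be falsely positive. A test of the treatment-by-time coefficient does reject very often under these assumptions: 39% to 93% with 12 weekly scores and a coefficient falling from 0.7 to 0.3, for D from 0.2 to 0.5. But 11.4 names no such test; it reports daily contrasts. A reader might also infer that those contrasts are unadjusted, or biased towards PNF. Neither follows. With D = 0.5 and a day-1 coefficient of 0.7, the crude difference is 0.35 and the planned model leaves 0.10, so it removes (0.35 − 0.10)/0.35 = 71%. The direction depends on whether the coefficient rises or falls, which the Protocol does not indicate.

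**Conclusion.** The point holds as a conditional weakness of moderate size. As written, the model adjusts the daily PNF–LF differences for baseline score only on average over follow-up. Under the assumed imbalance (0.3–0.5 SD) and coefficient change (0.3–0.5 over 84 days), the remainder is about 0.05–0.12 SD on day 1, in either direction, and about 0.02–0.04 SD on day 28. Rejection on day 1 is about 10% to just over 40% instead of 5%, and 6–9% by day 28. These figures also rest on the assumed variance components, a linear coefficient change and balanced data. With equal baseline means there is no bias in the estimate, and with a constant coefficient there is neither bias nor inflation. The documents do not show that the bias will occur or which group it would favour. It merits correction because non-randomised groups may well differ, no planned analysis would reveal the problem, and the remedy is cheap.

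**What to change.** In section 11.4, add a baseline score-by-time interaction to the primary model and to every Objective 2 model, using the same time function as the treatment-by-time term, and derive the daily marginal means from that model. Age-by-time and sex-by-time can be added in the same way.

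The cost is one sentence, a few degrees of freedom and a negligible loss of precision if the baseline effect is in fact constant. No new data are needed.

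Two limits should be recognised. The change does nothing for confounders outside the model. Nor does it make up for the absence of random slopes: when simulated recoveries varied between people (slope SD 0.5 over follow-up), a random-intercept model with baseline-by-time still rejected the treatment-by-time coefficient in 14–15% of runs. That is a separate matter.

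### Section 11.4 does not fix the shape of time, and its wording points to a straight-line group difference, which does not suit hypotheses about the first 2 or 4 weeks.

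*Protocol*

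**What the plan says.** Section 11.4 says that the primary and secondary hypotheses "will be tested with mixed-effects linear modelling". The model has a random intercept for participant, fixed effects for age, sex and baseline score, and "an interaction term between time (number of days following the intervention) and treatment allocation". From it come marginal means, with "between-group differences calculated at daily timepoints after Tukey adjustment for multiplicity", and the differences are set against a "minimal important difference (MID) estimate of half a standard deviation of baseline scores". The outcome is labelled continuous. Time carries no such label, and no functional form is given for it.

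Section 6 states the primary prediction as different trajectories over 12 weeks, "with less severe post-treatment symptoms in the PNF group within the first 4 weeks". Two secondary comparisons (open against minimally invasive carpal tunnel decompression, and open release against injection for trigger finger) concern the first 2 weeks. Section 7 describes the primary cohort as participants "who will be followed up for a 12-week period with daily EMCAT assessments".

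Section 11.3 says: "There is not a separate SAP document in use for the trial". Section 11.10, which deals with missing data, plans no sensitivity analyses.

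**The concern.** A count of days with one interaction term is most naturally read as a numeric covariate. Each treatment group then has one straight line, and the difference between groups is also a straight line. The estimate for days 1 to 28 is then partly set by days 29 to 84, which are two thirds of the follow-up.

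The daily differences are the primary result and are compared with the minimal important difference (MID). The study collects daily scores in order to see early differences that sparse measurement might miss, and a straight line discards that detail. The trigger finger hypothesis is the most exposed, because it predicts that the difference is not clinically important: a model that shrinks a short early difference makes that prediction easier to confirm. With no separate SAP, Section 11.4 is the only place where the form of time can be settled.

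**Working it through.** **Inputs from the protocol.** Planning effect 0.35 with SD 1, 90% power, 5% level, 172 per group (Section 11.5); 84 daily assessments (Section 7); MID of half a baseline SD (Section 11.4).

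**Assumptions.** The shape of the true difference, complete data, baseline SD of 1, and two-sided testing. The protocol gives none of these.

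**1. The plan's own figure.** n per group = 2(1.960 + 1.282)² / 0.35² = 171.5, so 172 per group and 344 in all. This reproduces Section 11.5. It is a single comparison of two means with no time term, so it does not depend on the point raised here.

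**2. Formula for the fitted difference.** With complete balanced data, the random-intercept model with linear day by treatment estimates the least-squares line through the true daily differences d(t), t = 1 to 84. The mean day is 42.5 and S = Σ(t − 42.5)² = 49,385. Slope b = Σ(t − 42.5)d(t) / S, and the fitted value at day t is mean(d) + b(t − 42.5).

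**3. Step of 0.35 SD on days 1 to 28, then zero.**
- mean(d) = 0.35 × 28/84 = 0.1167
- Σ(t − 42.5) over days 1 to 28 = 28 × (14.5 − 42.5) = −784, so b = 0.35 × (−784)/49,385 = −0.005556
- Fitted mean, days 1 to 28: 0.1167 + 0.005556 × 28 = **0.27** (truth 0.35)
- Day 1: 0.1167 + 0.005556 × 41.5 = 0.35 (truth 0.35)
- Day 28: 0.1167 + 0.005556 × 14.5 = 0.20 (truth 0.35)
- Day 84: 0.1167 − 0.005556 × 41.5 = **−0.11** (truth 0)

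**4. Step of 0.5 SD on days 1 to 14, then zero (the 2-week hypotheses).**
- mean(d) = 0.5 × 14/84 = 0.0833
- Σ(t − 42.5) over days 1 to 14 = 14 × (7.5 − 42.5) = −490, so b = 0.5 × (−490)/49,385 = −0.004961
- Fitted mean, days 1 to 14: 0.0833 + 0.004961 × 35 = **0.26** (truth 0.50)
- Day 1, the highest fitted value: 0.0833 + 0.004961 × 41.5 = 0.29

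The highest fitted value is thus 0.29/0.50 = 0.58 of the step. A two-week step of up to about 0.5/0.578 = 0.86 SD would lie below a 0.5 SD MID on every fitted day.

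**5. Other shapes (peak = 1; true / fitted).**

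| Shape of true difference | Day 1 | Mean days 1-28 | Day 28 | Day 84 |
|---|---|---|---|---|
| Step, days 1-28 | 1.00 / 0.99 | 1.00 / 0.78 | 1.00 / 0.56 | 0 / −0.33 |
| Linear fade to 0 at day 28 | 1.00 / 0.55 | 0.50 / 0.43 | 0 / 0.30 | 0 / −0.22 |
| Exponential, half-life 10 days | 0.93 / 0.49 | 0.43 / 0.38 | 0.14 / 0.28 | 0.00 / −0.16 |
| Exponential, half-life 28 days | 0.98 / 0.81 | 0.71 / 0.69 | 0.50 / 0.56 | 0.12 / 0.02 |
| Linear fade to 0 at day 84 | 0.99 / 0.99 | 0.83 / 0.83 | 0.67 / 0.67 | 0 / 0 |

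**6. General result.** For any one-directional difference confined to days 1 to 28, the fitted mean over those days is 0.56 to 0.99 of the truth. For one confined to days 1 to 14, the fitted mean over days 1 to 14 is 0.45 to 0.58 of the truth. In the fitted value at day 84, every day before day 28.3 has negative weight, so a difference confined to days 1 to 28 always shows the reversed sign there.

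**7. How often the reversal would be nominally significant.** Simulation with 172 per group, total SD 1, intraclass correlation 0.5 or 0.7, an unadjusted 1.96 cut-off and 400 runs per setting. With a peak of 0.35 SD, the day-84 difference was significant in the wrong direction in 7% to 30% of runs across the step, the linear fade to day 28 and the exponential with half-life 10 days.

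**The case against.** The strongest reply is that the protocol never calls time linear or continuous. A linear mixed model is linear in its parameters and can hold day as a factor or a spline. Daily contrasts and plotted marginal means fit a day factor at least as well as a line, and a day factor has none of this bias. That stands: a straight line is the natural reading of the wording, not a stated fact.

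Second, the protocol predicts nothing for weeks 5 to 12. A reader might infer that the hypothesis says the difference vanishes after week 4, but Section 6 does not say so. With slow fading the bias is small or nil, as the last two rows of the table show.

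Third, it is tempting to say that the early difference is shrunk throughout. It is not. A 28-day step is almost unshrunk at day 1, and a fading difference is overstated near day 28. What is too small is the early average.

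Fourth, a reader might infer that the study would wrongly conclude in favour of fasciectomy at week 12. At the planning effect the day-84 value is about −0.05 to −0.11 SD, below the half-SD MID if the baseline SD is near 1, usually not significant, and at a time for which Section 6 makes no specific prediction.

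None of this removes the need for a clear statement. The two readings give different primary results, and nothing in the protocol chooses between them.

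**Conclusion.** The point holds in this form: Section 11.4 leaves the form of time open, its wording points to a straight line, and a straight line does not suit hypotheses about the first 2 or 4 weeks. If the difference is concentrated early, the average early difference is understated: 0.27 for a true 0.35 SD over 4 weeks, and 0.26 for a true 0.5 SD over 2 weeks. The direction of that error does not depend on the assumed variances. Its size depends on the shape of the true difference, which the protocol does not give.

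The documents do not support the stronger statements that the plan certainly fits a straight line, that a false late reversal would become a study conclusion, or that the sample size of 172 per group is affected. The wording should be settled before analysis.

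**What to change.** Add one sentence to Section 11.4: time since treatment is modelled flexibly and interacted with treatment, either as a natural cubic spline of day with knots concentrated in the first 4 weeks (including the first 2), or with day as a factor. Both keep the planned daily marginal differences. A single change of slope at day 28 is not enough: for a step with peak 1 it gives 1.31 at day 1 and −0.17 at day 84. If the sponsor already intends day as a factor, the sentence only has to say so.

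**Cost.** A spline adds a few parameters. A day factor needs 83 time terms and 83 interaction terms, which 344 × 84 = 28,896 planned assessments can carry. Daily intervals become wider. With total SD 1 and 172 per group, the standard error of a daily difference under a day factor is √(2/172) = 0.108. Under a straight line at day 1 it is √[(2/172) × (ICC + (1 − ICC)(1/84 + 41.5²/49,385))], which is 0.078 for an intraclass correlation (ICC) of 0.5 and 0.091 for 0.7. A spline should fall between the two. No change to data collection or sample size is needed.
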